1.4.1 Hypotheses

- Consolidation with 4 cycles of IRD will be well tolerated and will result in \geq 15% improvement in MRD-negative rate
- MRD-negativity after 4 cycles of IRD consolidation will be associated with an improved PFS and OS
- Maintenance therapy with ixazomib will be well tolerated and will be similar in response rate, PFS, OS, and MRD-positive to MRD-negative conversion rate to maintenance therapy with lenalidomide.

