15.1 Determination of Sample Size

A power analysis was performed for the primary objective. The smallest increase in MRD-negative rate after four cycles of IRD that would warrant further investigation is 10%, with a result of $\leq 9\%$ being considered ineffective. Based on a meta-analysis of five prior studies in this population, the expected MRD-negative rate at Day 100 post-transplant is ~50%. If the true rate of MRD-negative is 40-60% at the Day 100 post-transplant visit, 220 evaluable patients will detect a 10% improvement in MRD-negative rate with 90% power at 1-sided 0.05 alpha. Due to highly varied data of baseline MRD (i.e., 5 published studies showed MRD-negative rates ranged from 8% to 62%) as well as the lack of pilot information for the association over time, we currently choose a rather conservative estimation and the sample size is estimated using non-paired design instead. However, an interim analysis will be performed when ~50 patients are randomized to maintenance arms, and sample size adjustment will then be made if needed (see details below for interim analysis).

The randomized maintenance portion of the study will provide pilot data that will be used to design future studies. Although the study was not powered to show non-inferiority or superiority of either of the two maintenance arms, the designed sample size (n=110 evaluable patients/arm) will provide us a reasonable power for our hypothesis that "Maintenance therapy with ixazomib will be well tolerated and will be similar in response rate, PFS, OS, and MRD-positive to MRD-negative conversion rate to maintenance therapy with lenalidomide". Taking PFS as an example, the recent meta-analysis of lenalidomide versus placebo/observation showed that the 5-year cumulative incidence of events (PD or 2nd-line treatment) was ~54%. [29] The figure below illustrates the statistical power to show non-inferiority given the "true" difference of event rates (e.g., death or recurrence or treatment failure) between the ixazomib arm (experimental group) and lenalidomide arm (control group). With a non-inferiority margin of 10% in 5-year PFS (or equivalently a hazard ratio (HR) of 1.3), for example, the designed sample size would allow 80% power to claim non-inferiority when a slightly better PFS is observed in the ixazomib arm.

This power analysis was based on a simulation study where

- the true rate in the experimental treatment (ixazomib) varied from 45% to 65%;

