- the true recurrence rate in the control (lenalidomide) varied from 52% to 56%;
- a total of 10,000 replicates are generated under each scenario, and each replicate includes N=110 ixazomib patients and N=110 lenalidomide patients;
- events in each arm were generated following binomial distributions;
- 1-sided 90% confidence interval (CI) for the difference between event rates was calculated and non-inferiority will be declared if the upper boundary of CI is below 10% [30]. That is, the non-inferiority margin was set as 10% absolute difference, or equivalently a hazard ratio (HR) of 1.3 when assuming the time following an exponential distribution;
- The figure shows average power as a function of the true difference of event rates between experimental and control groups;
- Note that the current simulation was based on binary data for simplicity. We expect that more power could be achieved in the actual time-to-event analysis due to the availability of richer information (i.e., not only the status of event, but also the exact time when it happens).

The accrual rate over six participating centers will be roughly 6 patients per month, with a total accrual timeframe of about 3 years following study activation.

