15.2 Randomization and Stratification

Following initial treatment with IRD consolidation therapy, patients will be randomized to a pilot portion of the study evaluating ixazomib or lenalidomide as maintenance therapy.

Patients will be restaged following completion of consolidation treatment and will be randomized on a 1:1 basis to maintenance therapy with ixazomib or lenalidomide. Patients will be stratified based on MRD status at restaging (MRD-negative v. MRD-positive). For the purposes of randomization, if there are discrepant results from the Mayo Clinic MFC and the Adaptive ClonoSEQ MRD tests, the Adaptive ClonoSEQ results will be used for stratification. In the event that the Adaptive ClonoSEQ results are not available, the Mayo Clinic MFC results will be used for stratification, and vice versa.

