15.3 Data Analysis

For the analysis of consolidation therapy, the data for safety analysis will include these patients who have at least 1 dose of IRD consolidation therapy, while the data for efficacy analysis will include patients who complete 4 cycles therapy. Demographic and clinical characteristics of the sample, as well as adverse events, complications and loss to follow-up will be summarized using descriptive statistics. The change of MRD-negative rates for pre- and post-consolidation therapy will be described using contingency table and compared by McNemar test. The incidences of mortality, progression, relapse, as well as tumor response (complete response and overall) and their 95% confidence intervals following consolidation therapy will also be calculated.

Data analysis for maintenance portion will be performed following the intent-to-treat (ITT) principle. The balance of demographic and baseline clinical characteristics between two arms will be compared using t-test, Mann-Whitney rank-sum test, or Chi-square test as appropriate. The distributions of responses and adverse events across two arms will be summarized using contingency tables and compared by 2-sample Chi-square test or Fisher's exact test. Contingency table and Fisher's exact test will also be used to assess the between-arms difference for the rates of conversion from MRD-positive to MRD-negative. Chi-square test will be used to compare the distribution of responses, and Kaplan-Meier curves with log rank tests will be used to compare PFS and OS.

Overall survival (OS) will be defined as time from ASCT to death due to any causes, and survivors will be censored at withdrawal or study closeout. Progression-free survival (PFS) will be defined as time from ASCT to progression, relapse, or death, whichever occurs first, and those event-free survivors will be censored at withdrawal or study closeout. The between-arm differences in OS and PFS will be described using Kaplan-Meier product limit estimator and compared by log-rank tests. Kaplan-Meier curves will also be used to describe the association between MRD status (both prior to and after consolidation therapy) and OS or PFS, and proportional hazards Cox models will be used to control the potential confounding effects of other patient and clinical characteristics.

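### The final maintenance-arm analysis in Section 15.3 compares PFS and OS only by Kaplan-Meier and unstratified log-rank tests, without the effect measure, confidence bound and margin of 15.1 and 15.4

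*Combined protocol and SAP*

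**What the plan says.** Section 1.4.1 expects that ixazomib maintenance "will be similar in response rate, PFS, OS, and MRD-positive to MRD-negative conversion rate to maintenance therapy with lenalidomide", and 15.1 repeats this. Section 15.1 then works in non-inferiority terms: "With a non-inferiority margin of 10% in 5-year PFS (or equivalently a hazard ratio (HR) of 1.3". Its power simulation uses a 1-sided 90% interval for the difference in event rates, and "non-inferiority will be declared if the upper boundary of CI is below 10" (per cent). The simulation is binary, but the section looks ahead: "We expect that more power could be achieved in the actual time-to-event analysis". Section 15.1 also says that "the study was not powered to show non-inferiority or superiority of either of the two maintenance arms", and 15.2 calls this a pilot portion.

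Section 15.2 states: "Patients will be stratified based on MRD status at restaging (MRD-negative v. MRD-positive".

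Section 15.4 describes PFS and OS differences by hazard ratio at the Year-4 and Year-6 looks, with survival curves and their confidence intervals, and takes an observed HR of 1.3 as the futility threshold.

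For the final analysis, 15.3 says "Kaplan-Meier curves with log rank tests will be used to compare PFS and OS" and later "The between-arm differences in OS and PFS will be described using Kaplan-Meier product limit estimator and compared by log-rank tests". The 95% intervals in 15.3 are for incidences after consolidation. Its Cox models stand in the sentence on MRD status and outcome, not in the arm comparison. No significance level is given for the log-rank tests.

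**The concern.** As written, the final analysis specifies less about the arm difference than the interim looks do. A log-rank test asks whether the curves differ. Failing to reject does not show that they are close, least of all at this sample size. A result that misses the plan's own margin could therefore be reported as no significant difference, beside a hypothesis of similarity.

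Sections 1.4 and 15.1 say that these data will help to design later studies, including a larger phase III trial. That use needs an effect size with its uncertainty, on a scale and at a time point chosen beforehand.

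A smaller, separate matter is that the PFS/OS arm comparison is not stratified by restaging MRD status, although randomisation is and 1.4.1 expects that status to be prognostic. Leaving a prognostic stratum out makes the log-rank test somewhat conservative and gives a marginal HR that is closer to 1 than the within-stratum HR.

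**Working it through.** **1. The plan's own figures (15.1, 15.4).** Inputs: 110 per arm, control 5-year event rate 54%, margin 10 points, 1-sided 90% bound (z = 1.2816). With d = ixazomib rate minus control rate and SE = √[p_c(1−p_c)/110 + p_t(1−p_t)/110], power = Φ((0.10 − d)/SE − 1.2816).
- d = 0: 58%
- d = −4 points: 79%
- d = −4.5 points: 81%
- d = −5 points: 83%

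The stated 80% is reached when the ixazomib event rate is 4 to 4.5 points lower, which fits the plan's slightly better PFS. The margin is also coherent: ln(0.36)/ln(0.46) = 1.316, and HR 1.3 turns 54% into 1 − 0.46^1.3 = 63.6%, a rise of 9.6 points. The rises of about 3 and 6 points quoted in 15.4 compute as 3.6 and 6.2.

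**2. Assumed event numbers.** The documents give no expected number of events. Assume exponential times with rate −ln(0.46)/5 = 0.1553 per year, and all 220 patients randomised. Events = 220 × (1 − e^(−0.1553t)), SE(log HR) = 2/√events, and the bound is exp(ln HR + 1.2816 × SE).

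| Follow-up (years) | Events | SE | Two-sided p at observed HR 1.20 | 1-sided 90% upper bound at observed HR 1.20 | Largest observed HR with bound below 1.3 |
|---|---|---|---|---|---|
| 4 | 102 | 0.198 | 0.36 | 1.55 | 1.01 |
| 5 | 119 | 0.183 | 0.32 | 1.52 | 1.03 |
| 7 | 146 | 0.166 | 0.27 | 1.48 | 1.05 |
| 8.5 | 161 | 0.158 | 0.25 | 1.47 | 1.06 |

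The 1-sided p at HR 1.20 is 0.12 to 0.18, so the result is also non-significant at 1-sided 0.05 and 0.10.

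**3. Where the log-rank test and the margin disagree.** At 119 events, observed HRs from 1.03 up to exp(z × 0.1835) are non-significant but fail the margin. The upper limit is 1.43 at two-sided 0.05, 1.35 at 1-sided 0.05 and 1.27 at 1-sided 0.10.

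**4. Ixazomib truly worse by the margin (HR 1.3).** Events at 5 years = 110 × 0.54 + 110 × 0.636 ≈ 129. SE = 2/√129.3 = 0.176, and ln(1.3)/SE = 1.49. Log-rank power = Φ(1.49 − z): 32% (two-sided 0.05), 44% (1-sided 0.05), 58% (1-sided 0.10).

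The futility rule in 15.4 would catch many such trials. In simulations with assumed looks at 25–50 and 60–100 events and a final analysis at 102–161 events, 62–64% met the stopping threshold first. A further 25–28% ran to the end, were non-significant at two-sided 0.05 and did not meet the margin (16–22% at 1-sided 0.10).

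**5. The MRD stratum.** Assumed: 40% MRD-positive, 54% control events at 5 years, treatment HR 1.3, two-sided 0.05, 6,000 simulated trials. Neither the MRD split nor the MRD hazard ratio is in the documents.

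| MRD HR | Level, unstratified v stratified | Power | Estimated HR |
|---|---|---|---|
| 2 | 4.4% v 5.3% | 30% v 33% | 1.29 v 1.31 |
| 3 | 3.5% v 4.9% | 25% v 32% | 1.26 v 1.30 |

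**6. The margin on the stratified scale.** Solve 0.6(1 − e^(−5λ)) + 0.4(1 − e^(−5kλ)) = 0.54, where k is the MRD HR, then multiply both hazards by 1.3. The overall 5-year event rate rises by 9.1 points (k = 2) or 8.3 points (k = 3), against 9.6 without strata. A within-stratum HR of 1.3 is thus a slightly tighter margin than the one in 15.1.

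**The case against.** The strongest reply is that this is a declared pilot, not powered for non-inferiority or superiority, and that the margin, the interval and the intention to analyse event times are all in the same chapter. No section says that a non-significant log-rank test will be read as similarity, and a hazard ratio can be added at reporting. Much of this stands. It fixes the weight of the point: the plan has a margin, and what is missing is its use in 15.3. It does not remove the point. The decision rule in 15.1 sits inside a description of a simulation on binary data, and nothing says which scale, time point or interval the final time-to-event analysis will use.

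A reader might infer that 15.3 ignores MRD status altogether. It does not: it relates MRD status before and after consolidation to PFS and OS, and compares MRD conversion between arms, which by definition concerns MRD-positive patients. Only the PFS/OS arm comparison is unstratified.

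It is also fair to say that stratifying is partly a change of estimand. The marginal HR is not wrong, and comparing a stratified HR with 1.3 would quietly move the margin (step 6). The fix therefore keeps the margin on the marginal scale.

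The event numbers can be questioned too. The 18-month follow-up limit in 5.8 and the patients assigned without randomisation under 5.1 both lower them, and 8.5 years exceeds the roughly 7 years of participation in the Protocol Summary. Fewer events would widen the gap between non-significance and similarity.

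**Conclusion.** The point holds as a gap in the specified final analysis. Section 15.3 does not carry the effect measure, the 1-sided 90% bound and the margin into the final PFS/OS comparison, and does not stratify that comparison by the randomisation factor. With 102 to 161 assumed events, an observed HR must be about 1.01 to 1.06 or lower to clear 1.3, while much larger values remain non-significant. Stratifying adds between 3 and 8 percentage points of power under assumed MRD hazard ratios of 2 to 3, so it is secondary.

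Two stronger readings are not supported. One is that a required confirmatory non-inferiority test has been left out: 15.1 and 15.2 rule that out by calling this portion a pilot. The other is that the 80% power is wrong: it reproduces on the plan's own binary scale.

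The sizes rest on exponential times, the plan's 54% control rate and assumed follow-up. The futility figures rest on assumed look timings. The logical point, that non-significance is not similarity, needs none of these. The change should be made, but the trial's design does not depend on it.

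**What to change.** Add to 15.3, for randomised patients and labelled as pilot evidence:

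1. Report the between-arm PFS hazard ratio with its 1-sided 90% upper bound against 1.3, and the 5-year Kaplan-Meier PFS difference with its 1-sided 90% bound against 10 points. Both stay on the marginal scale of 15.1. Report the OS hazard ratio with a confidence interval.
2. Use the log-rank test stratified by MRD status as recorded at randomisation, and state its level. Give the MRD-stratified Cox hazard ratio alongside, noting that it is stratum-specific and that 1.3 on that scale corresponds to about 8 to 9 points under the assumptions in step 6.
3. State that a non-significant log-rank test will not be interpreted as similarity.
4. Report patients assigned to an arm without randomisation under 5.1 separately.

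Section 15.1 needs no change. The cost is a few sentences and slightly more analysis, since the stratum and the event dates are already collected. Two hazard ratios will appear side by side, so the text must say that the marginal one is set against 1.3.

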15.4 Interim Analysis

Two interim analyses will be performed during the consolidation phase of the trial. The first will occur when ~50 patients complete the consolidation therapy and are randomized to maintenance portion. The second will occur in Year-3, after approximately 150 evaluable patients complete the consolidation therapy and are randomized to maintenance portion.

The data analysis will be descriptive in nature. The change of MRD-negative rates for pre- and post-consolidation therapy will be estimated using contingency table. Sample size will be re-estimated and conditional power will also be calculated based on the accumulated data. Conditional power is defined as the projected power to reject the null hypothesis at the end of study given the data accrued up to a specific interim analysis.

Therefore, a high value of conditional power indicates a highly likely, if not inevitable, conclusion to reject the null hypothesis given the available information. Similarly, a small value suggests a high possibility of negative finding given the current data. This interim analysis will assist investigators on the decision whether the sample size (220 evaluable, ~240 total) needs to be adjusted.

Two additional interim analyses will also be scheduled to monitor the futility of maintenance portion and thus to reduce the exposure of patients to inferior treatment. The first will occur in Year-4 (i.e., near the end of accrual period) and the other at Year-6 (i.e., when all patients have at least 2-year follow-up of maintenance therapy). Each interim analysis will be descriptive in nature. The rates of conversion from MRD-positive to MRD-negative across different arms will be summarized using contingency tables and compared by Fisher's exact test. The differences in PFS or OS between arms will be described using hazard ratios (HR). Kaplan-Meier product limit method will also be used to estimate survival curves and the corresponding confidence intervals. The stopping rule for an early termination due to futility will follow the guidelines for non-inferiority trials. [31] That is, the study will be recommended for an early termination whenever the observed HR is equal or worse than 1.3 (the non-inferiority margin) and the outcome is in favor of lenalidomide (control arm). For PFS, for example, the recent meta-analysis showed that the 1-year and 2-year event rates in the lenalidomide cohort are 13% and 25%, respectively, and HR=1.3 corresponds to an increase of ~3% and ~6% for 1-year and 2-year event rates.

16.0 MULTICENTER REGULATORY REQUIREMENTS

Washington University requires that each participating site sends its informed consent document to be reviewed and approved by the Washington University Regulatory Coordinator (or designee) prior to IRB/IEC submission.

Each participating institution must have the following documents on file at Washington University prior to first subject enrollment:

- Documentation of IRB approval of the study in the form of a letter or other official document from the participating institution's IRB. This documentation must show which version of the protocol was approved by the IRB.
- Documentation of IRB approval of an informed consent form. The consent must include a statement that data will be shared with Washington University, including the Quality Assurance and Safety Monitoring Committee (QASMC), the DSMC (if applicable), and the Washington University study team.
- Documentation of FWA, signed FDA Form 1572, and signed and dated CVs of all participating investigators.
- Documentation of training in protection of human subjects by all participating investigators.
- Protocol signature page signed and dated by the investigator at each participating site.

The Principal Investigator is responsible for disseminating to the participating sites all study updates, amendments, reportable adverse events, etc. There will be one current version of the protocol document at any given time and each participating institution will utilize that document. Protocol/consent modifications and IB updates will be forwarded electronically to the secondary sites within 2 weeks of obtaining Washington University IRB approval with acknowledgement of receipt requested. Secondary sites are to submit protocol/consent/IB modifications to their local IRBs within 4 weeks of receipt, and confirmation of submission must be forwarded to the appropriate contact person on the Washington University study team at the time of submission. Upon the secondary sites obtaining local IRB approval, documentation of such shall be sent to the Washington University study team within 2 weeks of receipt of approval.

Documentation of participating sites' IRB approval of annual continuing reviews, protocol amendments or revisions, all SAE reports, and all protocol violations/deviations/exceptions must be kept on file at Washington University.

The investigator or a designee from each institution must participate in a regular conference call to update and inform regarding the progress of the trial.

We would like to thank the Alvin J. Siteman Cancer Center at Washington University School of Medicine and Barnes-Jewish Hospital in St. Louis, Missouri, for the use of the Clinical Trials Core which provided protocol development and study coordination services. The Siteman Cancer Center is supported in part by an NCI Cancer Center Support Grant #P30 CA91842.

APPENDIX A: ECOG Performance Scale

Grade	Description
0	Normal activity. Fully active, able to carry on all pre-disease performance without restriction.
1	Symptoms, but ambulatory. Restricted in physically strenuous activity, but ambulatory and able to carry out work of a light or sedentary nature (e.g., light housework, office work).
2	In bed <50% of the time. Ambulatory and capable of all self-care, but unable to carry out any work activities. Up and about more than 50% of waking hours.
3	In bed >50% of the time. Capable of only limited self-care, confined to bed or chair more than 50% of waking hours.
4	100% bedridden. Completely disabled. Cannot carry on any self-care. Totally confined to bed or chair.
5	Dead.

APPENDIX B: Cockcroft-Gault Equation

For males:

$$\text{Creatinine Clearance} = \frac{(140 - \text{age}[\text{years}] \times \text{weight} [\text{kg}])}{72 \times (\text{serum creatinine}[\text{mg/dL}])} \quad \text{OR} \quad \frac{(140 - \text{age}[\text{years}] \times \text{weight} [\text{kg}])}{0.81 \times (\text{serum creatinine}[\mu\text{mol/L}])}$$

For females:

$$\text{Creatinine Clearance} = \frac{0.85 (140 - \text{age}[\text{years}] \times \text{weight} [\text{kg}])}{72 \times (\text{serum creatinine}[\text{mg/dL}])} \quad \text{OR} \quad \frac{0.85 (140 - \text{age}[\text{years}] \times \text{weight} [\text{kg}])}{0.81 \times (\text{serum creatinine}[\mu\text{mol/L}])}$$

Source: Cockcroft DW, Gault MH. Prediction of creatinine clearance from serum creatinine. *Nephron* 1976;16(1):31-41.

